6 WEEK ETDQ-7

Next to each question, circle the number that best describes how you feel.

During the past 1 month , how much of a problem was each of the following?	No problem		Moderate Problem			Severe Problem	
	1	2	3	4	5	6	7
Pressure in the ears?	1	2	3	4	5	6	7
Pain in the ears?	1	2	3	4	5	6	7
A feeling that your ears are clogged or "under water"?	1	2	3	4	5	6	7
Ear problems when you have a cold or sinusitis?	1	2	3	4	5	6	7
Crackling or popping sounds in the ears?	1	2	3	4	5	6	7
Ringing in the ears?	1	2	3	4	5	6	7
A feeling that your hearing is muffled?	1	2	3	4	5	6	7

Do you get these symptoms in one ear only or both ears?

Left ear only

Right ear only

Both ears

Change in eustachian tube symptoms and use of device

Please rate changes in your nasal symptoms and use of device.

Symptom	None	Mild	Moderate	High
Improvement in ear pressure	0	1	2	3
Improvement in ear clogging	0	1	2	3
Improvement in cracking/popping of ears	0	1	2	3
Improvement in muffled hearing	0	1	2	3
Improvement in tinnitus (noise in ears)	0	1	2	3
Improvement in ear pain	0	1	2	3
Improvement in ear problems with cold or sinus infection	0	1	2	3
Overall improvement in ear symptoms	0	1	2	3
Tolerability				
Pain with use of device	None	Mild	Moderate	Severe
Comfort and ease of use	Poor	Low	Moderate	High
Bleeding:	Yes	No		

Week 6 patient satisfaction

Would you use device again? Yes No

Would you recommend device to others? Yes No

AIM 3, SINUS PAIN/PRESSURE: Baseline Medical History and exam**SinuSonic Study****PI: [name]**

Subject ID#: _____ Subjects Initials: _____

DEMOGRAPHIC AND CLINICAL VARIABLES (If not previously collected):

Age at enrollment (years):

--	--

Gender: Male Female

What is/was your profession (current/retired)? _____

LANGUAGE, ETHNICITY, RACE, MARITAL STATUS**Please mark one of the following categories which describes your native language:**

- ☐ American English
- ☐ Other: please specify _____

Please mark one of the following categories which describes your ethnicity:

- ☐ Not Hispanic or Latino
- ☐ Hispanic or Latino

Please mark one or more of the following categories which describes your race:

- ☐ American Indian or Alaska Native
- ☐ Asian
- ☐ Black or African American
- ☐ Native Hawaiian or Other Pacific Islander
- ☐ White
- ☐ Other

SMOKING HISTORY**1. Do you currently smoke tobacco products? Yes No (If No please go to question 2)**

How many tobacco products do you use in a day? _____ Singles Packs

CURRENT MEDICATION USAGE

- | | | |
|---|------------------------------|-----------------------------|
|  Nasal steroid sprays (Flonase, Nasonex, etc) |  Yes |  No |
|  Nasal antihistamine spray (Astelin, etc) |  Yes |  No |
|  Oral antihistamines (Allegra, Claritin, Benedryl, etc) |  Yes |  No |
|  Oral decongestant (Sudafed, etc) |  Yes |  No |
|  Mucolytic (Mucinex, etc) |  Yes |  No |
|  Luekotriene (Singulair, etc) |  Yes |  No |

COMORBID MEDICAL CONDITIONS: Check box and provide details if present

- ☐ Depression history: ☐ Resolved/past diagnosis ☐ Present/medicated ☐ Present/not medicated
- ☐ Anxiety history: ☐ Resolved/past diagnosis ☐ Present/medicated ☐ Present/not medicated
- ☐ Obstructive Sleep Apnea: ☐ Currently being treated ☐ History / No current treatment
- ☐ Allergic rhinitis: _____
- ☐ Previous allergy testing (blood test or skin prick): ☐ Yes ☐ No
- ☐ Immunotherapy shots for allergies: ☐ Yes ☐ No ☐ Currently
- ☐ Non-allergic rhinitis ☐ Yes ☐ No
- ☐ Asthma ☐ Yes ☐ No
- ☐ Chronic rhinosinusitis ☐ Yes ☐ No
- ☐ Nasal polyps ☐ Yes ☐ No
- ☐ Viral respiratory infection ☐ Yes ☐ No
- ☐ Prior ear/sinus surgery ☐ Yes ☐ No
- ☐ Migraine headache history: ☐ Resolved/past diagnosis ☐ Present/medicated ☐ Present/not medicated

- _____
- ☐ Height (ft/in): _____
- ☐ Weight (lbs): _____

Rhinoscopy:

Septal Deviation: None Mild Moderate Severe Nasal

valve collapse: None Mild Moderate Severe Bleeding:

None Yes

[figure not shown]
Crusting: None Yes

Otoscopy: Normal Abnormal findings:_____

[figure not shown]
AIM 3, SINUS PAIN/PRESSURE: Baseline questionnaires

PATIENT QUESTIONS	
How long have you had sinus or facial pain/pressure? <3 months 3-6 months 6-12 months 1-3 year >3 years	
OVER THE LAST WEEK, HOW WOULD YOU RATE YOUR AVERAGE SINUS OR FACIAL PAIN/PRESSURE?	
	None possible Worst
Sinus or facial pain/pressure	◆—————◆

INCLUSION CRITERIA (all must be yes):Does patient have sinus pain/pressure for ≥ 3 mos? Yes NoIs VAS score ≥ 5 ? Yes No

AT THIS EXACT MOMENT, HOW WOULD YOU RATE YOUR SINUS OR FACIAL PAIN/PRESSURE?	
	
 None possible Worst 

Sinus or facial pain/pressure	
  

Place an X over an area where you typically experience sinus or facial pain/pressure (mark all that apply)

BASELINE Brief Pain Inventory-Short Form (BPI-SF)

2. Please rate your pain by circling the one number that best describes your pain at its worst in the last week.

0	1	2	3	4	5	6	7	8	9	10
No pain									Pain as bad as you can imagine	

3. Please rate your pain by circling the one number that best describes your pain at its least in the last week.

0	1	2	3	4	5	6	7	8	9	10
No pain									Pain as bad as you can imagine	

4. Please rate your pain by circling the one number that best describes your pain on average.

0	1	2	3	4	5	6	7	8	9	10
No pain									Pain as bad as you can imagine	

5. Please rate your pain by circling the one number that tells how much pain you have right now.

0	1	2	3	4	5	6	7	8	9	10
No pain									Pain as bad as you can imagine	

8. Circle the one number that describes how, during the past week, pain has interfered with your:

- a. General activity

0	1	2	3	4	5	6	7	8	9	10
Does not interfere									Completely interferes	

- b. Mood

0	1	2	3	4	5	6	7	8	9	10
---	---	---	---	---	---	---	---	---	---	----

- c. Walking ability

0	1	2	3	4	5	6	7	8	9	10
---	---	---	---	---	---	---	---	---	---	----

- d. Normal work (includes both outside the home and housework)

0	1	2	3	4	5	6	7	8	9	10
---	---	---	---	---	---	---	---	---	---	----

- e. Relations with other people

0	1	2	3	4	5	6	7	8	9	10
---	---	---	---	---	---	---	---	---	---	----

- f. Sleep

0	1	2	3	4	5	6	7	8	9	10
---	---	---	---	---	---	---	---	---	---	----

- g. Enjoyment of life

0	1	2	3	4	5	6	7	8	9	10
---	---	---	---	---	---	---	---	---	---	----

Does not interfere

Completely interferes

BASELINE McGill Pain Questionnaire – Short Form (MPQ-SF)

- 1) The words below describe average pain. Circle the one number that represents the degree to which you feel that type of pain.
Please limit yourself to a description of your pain in the **Sinuses or Face**

A. Throbbing:	None (0)	Mild (1)	Moderate (2)	Severe (3)
B. Shooting:	None (0)	Mild (1)	Moderate (2)	Severe (3)
C. Stabbing:	None (0)	Mild (1)	Moderate (2)	Severe (3)
D. Sharp:	None (0)	Mild (1)	Moderate (2)	Severe (3)
E. Cramping:	None (0)	Mild (1)	Moderate (2)	Severe (3)
F. Gnawing:	None (0)	Mild (1)	Moderate (2)	Severe (3)
G. Hot-Burning:	None (0)	Mild (1)	Moderate (2)	Severe (3)
H. Aching:	None (0)	Mild (1)	Moderate (2)	Severe (3)
I. Heavy:	None (0)	Mild (1)	Moderate (2)	Severe (3)
J. Tender:	None (0)	Mild (1)	Moderate (2)	Severe (3)
K. Splitting:	None (0)	Mild (1)	Moderate (2)	Severe (3)
L. Tiring-Exhausting:	None (0)	Mild (1)	Moderate (2)	Severe (3)
M. Sickening:	None (0)	Mild (1)	Moderate (2)	Severe (3)
N. Fearful:	None (0)	Mild (1)	Moderate (2)	Severe (3)
O. Punishing-Cruel:	None (0)	Mild (1)	Moderate (2)	Severe (3)

- 2) Please rate your **SINUS or facial** pain by circling the one number that tells how much pain you have **RIGHT NOW**.

0	1	2	3	4	5	6	7	8	9	10
No Pain										Pain as bad as you can imagine

- 3) Evaluate overall intensity of total pain experience. Please limit yourself to a description of the pain in your **SINUS area or face** only.
Place a check
mark (✓) in the appropriate column:

Evaluate		
0	No pain	
1	Mild	
2	Discomforting	
3	Distressing	
4	Horrible	
5	Excruciating	

AIM 3, SINUS PAIN/PRESSURE: Immediate (5 minute) Questionnaire

PATIENT QUESTIONS	
AFTER USING THE DEVICE, HOW WOULD YOU RATE YOUR SINUS OR FACIAL PAIN/PRESSURE?	
	None Worst possible
Sinus or facial pain/pressure	◆—————◆

AIM 3, SINUS PAIN/PRESSURE: 2 week Questionnaire

PATIENT QUESTIONS	
OVER THE LAST WEEK, HOW WOULD YOU RATE YOUR AVERAGE SINUS OR FACIAL PAIN/PRESSURE?	
	None Worst
	possible
Sinus or facial pain/pressure	◆—————◆

IMMEDIATELY AFTER USING THE DEVICE, HOW WOULD YOU RATE YOUR SINUS OR FACIAL PAIN/PRESSURE?	
	None Worst
	possible
Sinus or facial pain/pressure	◆—————◆

2 WEEK: Brief Pain Inventory-Short Form (BPI-SF)

2. Please rate your pain by circling the one number that best describes your pain at its worst in the last week.

0	1	2	3	4	5	6	7	8	9	10
No pain									Pain as bad as you can imagine	

3. Please rate your pain by circling the one number that best describes your pain at its least in the last week.

0	1	2	3	4	5	6	7	8	9	10
No pain									Pain as bad as you can imagine	

4. Please rate your pain by circling the one number that best describes your pain on average.

0	1	2	3	4	5	6	7	8	9	10
No pain									Pain as bad as you can imagine	

5. Please rate your pain by circling the one number that tells how much pain you have right now.

0	1	2	3	4	5	6	7	8	9	10
No pain									Pain as bad as you can imagine	

8. Circle the one number that describes how, during the past week, pain has interfered with your:

- a. General activity

0	1	2	3	4	5	6	7	8	9	10
Does not interfere									Completely interferes	

- b. Mood

0	1	2	3	4	5	6	7	8	9	10
---	---	---	---	---	---	---	---	---	---	----

- c. Walking ability

0	1	2	3	4	5	6	7	8	9	10
---	---	---	---	---	---	---	---	---	---	----

- d. Normal work (includes both outside the home and housework)

0	1	2	3	4	5	6	7	8	9	10
---	---	---	---	---	---	---	---	---	---	----

- e. Relations with other people

0	1	2	3	4	5	6	7	8	9	10
---	---	---	---	---	---	---	---	---	---	----

- f. Sleep

0	1	2	3	4	5	6	7	8	9	10
---	---	---	---	---	---	---	---	---	---	----

- g. Enjoyment of life

0	1	2	3	4	5	6	7	8	9	10
---	---	---	---	---	---	---	---	---	---	----

Does not interfere

Completely interferes

2 WEEK: McGill Pain Questionnaire – Short Form (MPQ-SF)

- 2) The words below describe average pain. Circle the one number that represents the degree to which you feel that type of pain.
Please limit yourself to a description of your pain in the **Sinuses or Face**

A. Throbbing:	None (0)	Mild (1)	Moderate (2)	Severe (3)
B. Shooting:	None (0)	Mild (1)	Moderate (2)	Severe (3)
C. Stabbing:	None (0)	Mild (1)	Moderate (2)	Severe (3)
D. Sharp:	None (0)	Mild (1)	Moderate (2)	Severe (3)
E. Cramping:	None (0)	Mild (1)	Moderate (2)	Severe (3)
F. Gnawing:	None (0)	Mild (1)	Moderate (2)	Severe (3)
G. Hot-Burning:	None (0)	Mild (1)	Moderate (2)	Severe (3)
H. Aching:	None (0)	Mild (1)	Moderate (2)	Severe (3)
I. Heavy:	None (0)	Mild (1)	Moderate (2)	Severe (3)
J. Tender:	None (0)	Mild (1)	Moderate (2)	Severe (3)
K. Splitting:	None (0)	Mild (1)	Moderate (2)	Severe (3)
L. Tiring-Exhausting:	None (0)	Mild (1)	Moderate (2)	Severe (3)
M. Sickening:	None (0)	Mild (1)	Moderate (2)	Severe (3)
N. Fearful:	None (0)	Mild (1)	Moderate (2)	Severe (3)
O. Punishing-Cruel:	None (0)	Mild (1)	Moderate (2)	Severe (3)

- 2) Please rate your **SINUS or facial** pain by circling the one number that tells how much pain you have **RIGHT NOW**.

0	1	2	3	4	5	6	7	8	9	10
No Pain										Pain as bad as you can imagine

- 3) Evaluate overall intensity of total pain experience. Please limit yourself to a description of the pain in your **SINUS area or face** only.
Place a check mark (✓) in the appropriate column:

Evaluate		
0	No pain	
1	Mild	
2	Discomforting	
3	Distressing	
4	Horrible	
5	Excruciating	

Week 2 patient satisfaction/safety

How much pain did you experience using device? None Mild Moderate Severe

Bleeding after using device? None Mild Moderate Severe

Would you use device again? Yes No

Would you recommend device to others? Yes No

AIM 3, SINUS PAIN/PRESSURE: 4 week Questionnaire

PATIENT QUESTIONS	
OVER THE LAST WEEK, HOW WOULD YOU RATE YOUR AVERAGE SINUS OR FACIAL PAIN/PRESSURE?	
	
 
None
 
Worst
 
 
 
possible
 

Sinus or facial pain/pressure	
 
◆
 
◆
 

IMMEDIATELY AFTER USING THE DEVICE, HOW WOULD YOU RATE YOUR SINUS OR FACIAL PAIN/PRESSURE?	
	
 
None
 
Worst
 
 
 
possible
 

Sinus or facial pain/pressure	
 
◆
 
◆
 

4 WEEK: Brief Pain Inventory-Short Form (BPI-SF)

2. Please rate your pain by circling the one number that best describes your pain at its worst in the last week.

0	1	2	3	4	5	6	7	8	9	10
No pain									Pain as bad as you can imagine	

3. Please rate your pain by circling the one number that best describes your pain at its least in the last week.

[illegible]

4. Please rate your pain by circling the one number that best describes your pain on average.

[illegible]

5. Please rate your pain by circling the one number that tells how much pain you have right now.

0 1 2 3 4 5 6 7 8 9 10
No pain Pain as bad as you can imagine

8. Circle the one number that describes how, during the past week, pain has interfered with your:

- a. General activity

0 1 2 3 4 5 6 7 8 9 10
Does not interfere Completely interferes

- b. Mood

0 1 2 3 4 5 6 7 8 9 10

- c. Walking ability

0 1 2 3 4 5 6 7 8 9 10

- d. Normal work (includes both outside the home and housework)

0 1 2 3 4 5 6 7 8 9 10

- e. Relations with other people

0	1	2	3	4	5	6	7	8	9	10
---	---	---	---	---	---	---	---	---	---	----

- f. Sleep

0 1 2 3 4 5 6 7 8 9 10

- g. Enjoyment of life

0 1 2 3 4 5 6 7 8 9 10

Does not interfere Completely interferes

4 WEEK: McGill Pain Questionnaire – Short Form (MPQ-SF)

- 3) The words below describe average pain. Circle the one number that represents the degree to which you feel that type of pain.
Please limit yourself to a description of your pain in the **Sinuses or Face**

A. Throbbing:	None (0)	Mild (1)	Moderate (2)	Severe (3)
B. Shooting:	None (0)	Mild (1)	Moderate (2)	Severe (3)
C. Stabbing:	None (0)	Mild (1)	Moderate (2)	Severe (3)
D. Sharp:	None (0)	Mild (1)	Moderate (2)	Severe (3)
E. Cramping:	None (0)	Mild (1)	Moderate (2)	Severe (3)
F. Gnawing:	None (0)	Mild (1)	Moderate (2)	Severe (3)
G. Hot-Burning:	None (0)	Mild (1)	Moderate (2)	Severe (3)
H. Aching:	None (0)	Mild (1)	Moderate (2)	Severe (3)
I. Heavy:	None (0)	Mild (1)	Moderate (2)	Severe (3)
J. Tender:	None (0)	Mild (1)	Moderate (2)	Severe (3)
K. Splitting:	None (0)	Mild (1)	Moderate (2)	Severe (3)
L. Tiring-Exhausting:	None (0)	Mild (1)	Moderate (2)	Severe (3)
M. Sickening:	None (0)	Mild (1)	Moderate (2)	Severe (3)
N. Fearful:	None (0)	Mild (1)	Moderate (2)	Severe (3)
O. Punishing-Cruel:	None (0)	Mild (1)	Moderate (2)	Severe (3)

- 2) Please rate your **SINUS or facial** pain by circling the one number that tells how much pain you have **RIGHT NOW**.

0	1	2	3	4	5	6	7	8	9	10
No Pain										Pain as bad as you can imagine

- 3) Evaluate overall intensity of total pain experience. Please limit yourself to a description of the pain in your **SINUS area or face** only.
Place a check mark (✓) in the appropriate column:

Evaluate		
0	No pain	
1	Mild	
2	Discomforting	
3	Distressing	
4	Horrible	
5	Excruciating	

Week 4 patient satisfaction/safety

How much pain did you experience using device? None Mild Moderate Severe

Bleeding after using device? None Mild Moderate Severe

Would you use device again? Yes No

Would you recommend device to others? Yes No

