- -Adults 18 years or older who complain of facial pain or pressure
- ≥ 3 months of symptoms duration (can be intermittent)
- Pain/pressure VAS score ≥ 5

Exclusion Criteria

- Sinonasal surgery within the last 3 months
- Grade 3-4 polyps
- Upper respiratory illness within last 2 weeks
- Topical decongestant use in last week
- Current nasal crusting or ulceration on rhinoscopy
- History of severe nose bleeding within last 3 months
- Known pregnancy
- Allergic sensitivity to silicone or any other component of device
- Inability to read and understand English
- Inability to perform treatment due to underlying medical condition

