6.0 Setting

Research will be conducted at the Medical University of South Carolina. Potential participant screening for all subjects across all aims, as well as baseline evaluations, will occur in the outpatient ENT clinics. For AIM 2, the 6-week post treatment assessment will take place in the outpatient ENT clinics. For AIM 3, follow-up measures will be collected remotely using REDCap at 2 and 4 weeks.

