9.1 Schedule of Events

Aim 1: NO in N=10 controls	Screening and baseline assessment
Day	0
Informed consent	X
Inclusion/exclusion criteria	X
Medical history	X
Rhinology, otoscopy	X
Vital signs	X
Exhaled nasalNO at 30 seconds and 5 min	X

Aim 2: ETD efficacy in N=30 patients	Screening and baseline assessment	Primary timepoint for outcomes
Week	0	6 + 1
Informed consent	X	
Inclusion/exclusion criteria	X	
Medical history	X	
Rhinology, otoscopy	X	X
Vital signs	X	
Distribution of Sinusonic	X	X
ETDQ-7	X	X
ETD VAS questionnaire	X	X
Tympanogram	X	X

Aim 3: Facial pain/pressure in N=30 patients	Screening and baseline assessment	Primary timepoint for outcomes	Secondary timepoint for outcomes
Week	0	2	4
Informed consent	X		
Inclusion/exclusion criteria	X		
Medical history	X		
Rhinology, otoscopy	X		

Vital signs	X		
Distribution of Sinusonic	X		
Pain/pressure VAS	X	X	X
BPI-SF	X	X	X
MPQ-SF	X	X	X

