12.0 Risks to Subjects

There is a risk of a loss of confidentiality of your personal information as a result of participation in this study.

There are risks to subjects using the SinuSonic device. Subjects may experience a degree of pain due to use of the device. This degree of pain is unknown. There may also be risk of nose bleeds or crusting around the nasal cavity.

The Rhinoscopy may activate the gag reflex. Additionally, nasal discomfort, nose bleeds, spasms, and coughing may also occur.

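### Nasal crusting, one of three named device risks, is neither asked about nor examined once Aim 3 home use starts, so 30 of 60 planned home users would have no systematic data on it

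*Combined protocol and SAP*

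**What the plan says.** **Named risks.** Section 12.0 gives three risks of using the device. One is pain: "Subjects may experience a degree of pain due to use of the device". The other two come together: "There may also be risk of nose bleeds or crusting around the nasal cavity". Confidentiality and the rhinoscopy procedure are listed there as separate risks.

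**Aim 3 follow-up.** Section 6.0 states: "For AIM 3, follow-up measures will be collected remotely using REDCap at 2 and 4 weeks". Section 9.1 marks the row "Rhinology, otoscopy" for Aim 3 at week 0 only.

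**Aim 3 safety questions.** In the Appendix, the week 2 and week 4 satisfaction/safety blocks each have four items. Two concern safety: "How much pain did you experience using device? None Mild Moderate Severe" and "Bleeding after using device? None Mild Moderate Severe". The other two ask whether the patient would use the device again and would recommend it.

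**Aim 3 baseline.** The baseline rhinoscopy form has a line "Crusting: None Yes". Section 4.0 excludes from Aim 3 anyone with "Current nasal crusting or ulceration on rhinoscopy".

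**Aim 2, for comparison.** Section 9.1 schedules the nasal and ear examination at weeks 0 and 6, and the six-week form records bleeding and crusting on rhinoscopy. The patient's own tolerability block on that form asks about pain, comfort and bleeding, not crusting.

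**General safety text.** Sections 9.0, 11.0 and 19.0 say that safety is monitored throughout the study. Sections 11.0 and 19.0 include nasal exams among the means. Section 19.0 requires all adverse events to be reported, whatever their seriousness or relationship to the device.

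**The concern.** Safety is part of the Aim 3 objective in section 1.0, and section 10.0 promises a summary of safety data at each time point. The plan chose to ask about two of the three named device risks at both Aim 3 follow-ups and left the third to chance. In Aim 2 an examiner looks for crusting after six weeks. In Aim 3 nobody looks after week 0 and nobody asks.

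The practical risk is in how the results are read. If the Aim 3 safety summary shows little or no crusting, a reader cannot tell whether it did not occur or was simply not sought. Crusting is often mild, and patients may not volunteer it as an adverse event.

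**Working it through.** The plan states no crusting rate and no safety sample-size figure, so there is nothing of its own to reproduce. The check is a comparison of risks with data fields, followed by short arithmetic.

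**Step 1. Match each named risk to what is collected after home use starts.**

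| Device risk (section 12.0) | Aim 2, week 6 | Aim 3, weeks 2 and 4 |
|---|---|---|
| Pain | self-report | self-report |
| Nose bleeds | self-report and rhinoscopy | self-report |
| Crusting | rhinoscopy | none |

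Two of the three risks have a post-use item in Aim 3. Crusting has none at either time.

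**Step 2. See whether another scheduled field fills the gap.** The only Aim 3 crusting field is on the baseline form. Because current crusting is an exclusion, every correctly enrolled patient has None there, and the field carries no information about home use. Section 15.0 pays up to $150 at $50 per visit in this group, that is 150 / 50 = 3 paid contacts. Section 6.0 nevertheless says the two follow-ups are remote, and section 9.1 puts no examination at either.

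**Step 3. Share of home users affected.** Section 5.0 plans 30 patients in Aim 2 and 30 in Aim 3. Aim 1 (10 healthy controls) is not a home-use group.

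30 / (30 + 30) = 30 / 60 = 50%.

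**Step 4. How many cases could be involved.** The documents give no rate, so the rates p below are assumptions shown as a range. Expected cases among the 30 Aim 3 patients are 30 × p, and the chance of at least one case is 1 − (1 − p)^30.

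| Assumed true rate | Expected cases | Chance of at least one |
|---|---|---|
| 5% | 1.5 | 1 − 0.95^30 = 79% |
| 10% | 3 | 1 − 0.90^30 = 96% |
| 20% | 6 | 1 − 0.80^30 = over 99% |

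These are cases that the week 2 and week 4 questions, as written, would not ask about. Some could still be reported as adverse events.

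**Step 5. What one added item would give.** With a self-report item answered by all 30 Aim 3 patients and no case reported, the exact two-sided 95% upper limit for self-reported crusting in that aim would be 1 − 0.025^(1/30) = 11.6%. Without the item there is no systematic Aim 3 denominator from which to form any limit.

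**Step 6. Set the monitoring text beside the schedule.** Sections 11.0 and 19.0 list nasal exams among the means of monitoring safety throughout the study. Section 9.1 gives Aim 3 one examination, at week 0, before home use. For Aim 3 the two do not agree.

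**The case against.** **General adverse event reporting covers crusting.** This is the strongest reply, and part of it stands. Section 19.0 takes in all adverse events, listings are reviewed at regular intervals, section 9.0 describes automated alerts for events of interest, and a coordinator telephones weekly. A reader might infer from the missing item that crusting cannot be recorded at all in Aim 3. The documents do not support that: it is unsolicited, not unrecordable. But the same adverse event route exists for pain and bleeding, and the plan still asks about those two directly. The stated purpose of the weekly calls is compliance. No adverse event form is among the documents, so whether it prompts for crusting is unknown.

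**The safety summary need not come from these forms.** A reader might infer that it will contain no crusting in Aim 3. Section 10.0 does not name its sources, and a reported adverse event would count as safety data. The summary may contain crusting; it will not contain a systematic count.

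**The forms follow a consistent split.** Crusting is recorded by an examiner everywhere in the Appendix, while patients report pain and bleeding. That is a fair reading, and it explains how the item came to be absent. It does not fill the gap in the one home-use aim that has no examiner after baseline.

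**Pooling the two aims.** A reader might infer that adding the item lowers the zero-event upper limit from 11.6% (n = 30) to 6.0% (n = 60). That would set rhinoscopy findings in 30 Aim 2 patients against self-report in 60. It would need equal risk under 6 and 4 weeks of use in different populations, full follow-up, and self-report that misses no case. The plan does not propose a pooled rate, and the comparison should not be made.

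**This is a pilot with no crusting endpoint.** True, and it limits the weight of the point.

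**Conclusion.** The point holds as a minor improvement. After home use starts in Aim 3, crusting is neither solicited nor examined, although section 12.0 names it as a device risk and safety is part of the aim. The size is 30 of 60 planned home users (50%) without systematic post-use crusting data, assuming both groups recruit as planned. How many cases could go unasked depends on a rate that the documents do not give: 1.5 to 6 expected cases for assumed rates of 5% to 20%.

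The mismatch between the nasal exams listed in sections 11.0 and 19.0 and the Aim 3 schedule in section 9.1 is a separate inconsistency. It must be reconciled whether or not the item is added.

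Neither aim has a control group, so any crusting rate would describe what happened during use and could not by itself be attributed to the device.

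**What to change.** 1. Add one row to the Aim 3 week 2 and week 4 safety questions: crusting or scabbing in or around the nose since the last form, answered None / Mild / Moderate / Severe. On the week 2 form the period runs from the start of device use.
2. Add the same row to the Aim 2 week 6 tolerability block, covering the period since device use started.
3. In the safety summary, report self-reported crusting by aim with its denominator, and show the Aim 2 rhinoscopy finding on a separate line. State that the recall periods differ between the aims.
4. Reconcile sections 9.0, 11.0 and 19.0 with section 9.1, so that the text says which safety assessments each aim has and when.

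The cost is one question on three existing forms, one row per aim in the safety table, and a text correction. Items 1 to 3 need no added visit, examination or staff. The downside is that self-report is less exact than rhinoscopy: it can miss crusting that the patient does not notice, and it can count other nasal debris as crusting.

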1.0 Objectives / Specific Aims

Aim 1: To determine if combined acoustic vibration and oscillating expiratory pressure impacts exhaled nasal Nitric Oxide (NO) in healthy controls as a potential mechanism

Aim 2: To determine the safety and efficacy of combined acoustic vibration and oscillating expiratory pressure for treatment of eustachian tube dysfunction (ETD).

Aim 3: To determine the safety and efficacy of combined acoustic vibration and oscillating expiratory pressure for treatment of sinus pain/pressure

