2.0 Background

Eustachian tube dysfunction (Meyer TA, etal) and sinus pain/pressure impact the quality of life of millions of Americans (Falco JJ, etal). It is thought that these disorders may be due to positive or negative pressure differential between the middle ear or paranasal sinuses. Current treatment options for ETD and sinus pressure/pain are typically Valsalva (positive expiratory pressure) with the hopes of equalizing pressures between the middle ear space or paranasal sinuses and the nasal cavity/external environment. Pharmacologically, nasal steroid sprays can be used to try to open the ET and sinus drainage pathways. If this fails, then procedures to include pressure equalization tubes (PETs) or balloon eustachian tube/paranasal sinus dilation are offered.

Future treatment options: This study aims to test the safety, efficacy and potential mechanism of action of the SinuSonic device on adults with ETD or facial pain/pressure. SinuSonic is a medical device that utilizes sound and pressure combined with normal breathing. It has been shown to be safe and relieve nasal congestion (Soler ZM, etal). The study will have 3 aims. Aim 1 will examine healthy controls with no signs of upper respiratory infection, inflammation, or ETD to determine if exhaled nasal NO is increased. Acoustic energy (humming) has been shown to increase nasal NO dramatically, thus equalization of gas pressures between the middle ear, the paranasal sinuses and the nasal cavity may very well explain any efficacy noted. Aim 2 will be performed to examine therapeutic efficacy for ETD. Aim 3 will be performed to examine therapeutic efficacy for sinus pain/pressure.

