5.0 Number of Subjects

Aim 1, exhaled NO: We anticipate 10 healthy control subjects for the exhaled NO portion of the study.

Aim 2, ETD: This is a pilot study. The anticipated ETD study population is 30 subjects.

Aim 3, Facial pain/pressure: This is a pilot study. The anticipated facial pain/pressure study population is 30 subjects.

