10.0 Data Management

All analyses and graphs will be performed with SPSS 24.0, Sample Power 3.0, and Sigma Plot 10.0 (SPSS, Chicago, IL.). Disease information and demographic variables, such as age, gender, race, quality of life (QOL) scores, and VAS scores will be summarized using frequencies, means, and standard deviation as appropriate. Aim 1 nasal NO metrics will be compared between baseline vs 10 seconds and baseline vs 3 minutes. Aim 2 metrics (ETDQ-7, ETD VAS and tympanogram) will be compared between baseline and 6 weeks. Aim 3 metrics (VAS, BPI-SF, MCQ-SF) will be compared between baseline vs 2 weeks and baseline vs 4 weeks. Categorical variables will be compared using Chi Square or McNemar's test. Continuous variables will be compared using One-Way ANOVA with repeated measures follow by post-hoc analysis. Data regarding safety and patient satisfaction will be summarized for each time point. A p-value ≤ 0.05 will be considered statistically significant. Due to the exploratory nature of this study, no p-value correction (ie Bonferroni) will be applied.

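### Aim 3 makes safety an objective, but its follow-up forms ask nothing about the ear, so most ear symptoms would be identified only if the patient volunteers them as adverse events

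*Combined protocol and SAP*

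**What the plan says.** Section 1.0 states the objective as "Aim 3: To determine the safety and efficacy of combined acoustic vibration and oscillating expiratory pressure for treatment of sinus pain/pressure". Section 2.0 offers a possible mechanism: "equalization of gas pressures between the middle ear, the paranasal sinuses and the nasal cavity may very well explain any efficacy noted". Section 5.0 gives the size: "The anticipated facial pain/pressure study population is 30 subjects".

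Under section 6.0, Aim 3 follow-up at weeks 2 and 4 is remote, through REDCap. The Aim 3 schedule in section 9.1 has otoscopy at week 0 only. In the appendix, the week 2 and week 4 satisfaction/safety blocks are identical. Each has a graded question on pain while using the device, a graded question on bleeding ("Bleeding after using device? None Mild Moderate Severe"), and two satisfaction questions.

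Section 19.0 requires every adverse event, whatever its seriousness or cause, to be reported from consent to the end of the study. Section 10.0 says that safety data will be summarized at each time point.

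For Aim 2, the week 6 tolerability rows cover pain ("Pain with use of device"), comfort and bleeding. The same visit also collects the ETDQ-7, the ear-symptom VAS, otoscopy, Valsalva and tympanogram type. Section 10.0 states: "Aim 2 metrics (ETDQ-7, ETD VAS and tympanogram) will be compared between baseline and 6 weeks".

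**The concern.** If a device may change middle-ear pressure, the ear is an obvious place to look for unwanted as well as wanted effects. Aim 2 looks there. Aim 3 uses the same device twice daily for 3 minutes over 4 weeks, which is 2 × 3 × 28 = 168 minutes of home use, and no follow-up question names the ear.

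Eligibility adds to this. Aim 2 excludes recent ear surgery, indwelling tubes, tympanic membrane perforation, a history of cholesteatoma or of the listed ear operations, patulous eustachian tube and Meniere's disease. The Aim 3 list contains none of these. The group that may include such ears is therefore the group that is not asked about them.

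At stake is what an Aim 3 safety statement can mean. If no ear complaints are reported, it will not be clear whether none occurred or none was mentioned.

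**Working it through.** The plan states no ear-event rate, safety sample size or power, so there is no figure to reproduce. The main check is of content.

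**1. How each ear symptom could be recorded in Aim 3 after baseline**
- *Ear pain during use.* The device-pain question has no site limit, so it would elicit and grade this pain, but would not show that it was in the ear.
- *Ear pain outside use.* The VAS asks about sinus or facial pain/pressure. The MPQ-SF tells patients to describe the sinuses or face only. The BPI-SF ratings, as printed, name no site, so ear pain could raise a score without being recognizable as ear pain.
- *Ear pressure outside use, muffled hearing, tinnitus.* No item on any Aim 3 follow-up form.
- *Signs on examination.* None, because follow-up is remote and otoscopy is at baseline only.
- *Remaining route.* General adverse-event reporting (section 19.0). The weekly calls in section 9.0 have compliance as their stated purpose. That section also mentions alerts for adverse events of interest, but the document does not list those events.

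**2. What asking would give with 30 patients**

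The true rates p below are assumptions. If every case is asked about and recorded, the chance of at least one case is 1 − (1 − p)^30:
- p = 2%: 45%
- p = 5%: 79%
- p = 10%: 96%

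If only half of cases are volunteered (a second assumption), the chance is 1 − (1 − 0.5p)^30:
- p = 2%: 26%
- p = 5%: 53%
- p = 10%: 79%

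With 0 of 30 recorded, the two-sided 95% exact upper limit is 1 − 0.025^(1/30) = 11.6%. Under full asking, that limits the true rate. Under half reporting it limits only the reported rate, and the matching true rate is 11.6% / 0.5, about 23%.

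**3. Aim 2: would a simple worsening count help?**

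Section 5.0 plans "The anticipated ETD study population is 30 subjects", with no control group. A natural tally would flag any patient who worsens by at least 1 point on any of the ETDQ-7 items for ear pain, ringing or muffled hearing. I simulated this with no device effect. The assumptions were: true levels uniform on 1 to 7, per-visit noise SD 0.5 to 1.0, error correlation between items 0 to 0.5, and answers rounded to whole points within 1 to 7. The share flagged was:
- 48% at SD 0.5 and correlation 0.5
- 72% at SD 1.0 and correlation 0

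That is about 14 to 22 of 30 patients (0.48 × 30 = 14.4; 0.72 × 30 = 21.6) flagged by noise alone. A 1-point rule cannot serve as a measure of harm here.

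**The case against.** The strongest reply is that the plan already has a safety net. All adverse events are collected in all aims, listings are reviewed periodically, a coordinator telephones every week, and safety data are summarized by time point. A patient troubled by new tinnitus may well mention it. The device-pain question would pick up ear pain during use. The mechanism is put forward as a possibility, section 12.0 names no ear risk, and this is a self-described exploratory pilot. All of that stands. It limits the point to symptoms that are not asked about, and it does not remove it: open reporting depends on the patient linking an ear symptom to a nasal device and choosing to mention it.

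A reader might infer three stronger things that the documents do not support.
- *That ear harm in Aim 3 cannot be captured, or that the protocol expects it.* Section 19.0 provides a route, and the middle-ear mechanism is hedged.
- *That Aim 3 ignores the ear altogether.* Baseline includes otoscopy and a box for prior ear or sinus surgery.
- *That ear worsening in Aim 2 is lost in a mean change.* Mean comparison applies to the ETDQ-7 and VAS. Tympanogram type is categorical and falls under Chi Square or McNemar's test, and otoscopy and Valsalva are recorded for each patient at week 6. An invented mix of improvers and worseners can give a significant mean improvement, but that holds for any trial and says nothing specific about this one. What Aim 2 lacks is a tabulation of data it already holds.

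**Conclusion.** The point holds for Aim 3 follow-up. Muffled hearing, tinnitus, and ear pain or pressure outside device use are not solicited, ear pain during use is not localized, and the ear is not examined after baseline. These symptoms would be identified only through unsolicited adverse-event reports, which are likely to under-count them. The size of the under-count cannot be derived from the documents. The 79% against 53% comparison rests on an assumed 5% rate and assumed half reporting, and only illustrates the effect.

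Even with the items added, 30 patients with no events would leave rates up to 11.6% compatible with the data, so the gain is in knowing what was asked, not in precision. For Aim 2 there is no comparable gap in collection, and fuller reporting is optional.

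**What to change.** **Aim 3.** Add three separate items to the week 2 and week 4 REDCap safety block, each covering new or worse symptoms since starting the device and each graded None / Mild / Moderate / Severe: ear pain or pressure; muffled hearing; ringing in the ears. In section 10.0, state that each will be summarized at each time point as number and percentage with an exact 95% confidence interval.

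**Aim 2 (optional, descriptive only).** Tabulate the baseline-to-week-6 shift in tympanogram type and in otoscopy as full cross-tables, so that every transition shows, including C to B. Show the distribution of individual ETDQ-7 changes in both directions. Do not label a 1-point worsening on a single item as harm, because there is no control group and that threshold mostly reflects measurement noise.

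**Cost.** Three short questions on two existing remote forms, one added line in section 10.0, and, if wanted, tables from Aim 2 data already collected. No new visit and no larger sample. The downside is slightly longer forms.
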